## 5. STATISTICAL AND ANALYTICAL PLANS

## 5.1. Disposition of subjects

The following descriptions (number and percentage of subjects) will be performed with regards to the disposition of subjects:

- Subject overall disposition on the Extended Set for each subset separately:
  - Subjects present at each study visit by contrast agent, sequence and globally.
  - Subjects screened, subjects randomized, subjects administered at the first MRI procedure, subjects administered at the second MRI procedure and subjects who completed the study by contrast agent, sequence and globally.
  - Subjects screen failure, reasons of screen failure, premature discontinuation from the study before receiving the 1st and the 2nd contrast agent and reasons why subjects were prematurely discontinued by contrast agent, sequence and globally.
- Subjects globally recruited in each center sorted by country on the Extended Set.

The tables that will be displayed are detailed in Section 6.1.1.1 and the listings in Section 6.2.1.

## 5.2. Data Sets Analysed and protocol deviations

### 5.2.1. Data Sets Analysed

There will be four subject sets defined for this study: the Extended Set, the Safety Set, the FAS and the PPS.

The Extended Set will include all subjects having signed the Informed Consent Form (ICF). This set will be used for subject disposition summaries, overall summary of AEs and individual listings.

The Safety Set will include all subjects, receiving at least one injection of contrast agent, regardless of the quantity. Subjects of subset 1 will be included in this set. This set will be used for description of demographic data, medical history, previous treatments and evaluation of safety. Analyses using the Safety Set will be based on the contrast agent actually received.

The FAS will include all subjects from subset 2 who have a CNR from both enhanced and unenhanced measurements derivable from one MRI by at least one off-site blinded reader. This set will be used for description of demographic data, baseline characteristics data, medical history, previous treatments and evaluation of efficacy. Analyses using the FAS will be based on the contrast agent allocated by the randomization whatever the contrast agent actually received, following the Intention To Treat (ITT) principle.

The PPS will be a subset of the FAS and will include all subjects who have no major protocol deviations (see below) throughout their whole study period. This set will be used for the evaluation of the primary efficacy criterion and main secondary criteria.

CONFIDENTIAL	
FORM
 
STATISTICAL ANALYSIS PLAN N° GDX-44-004
 
VERSION 1.0      DATED: 09JAN2018
	[REDACTED]
--------------	---	------------

Page 19 / 60

Analysis data sets will be presented on the Extended Set: subjects included in the Safety Set by contrast agent actually received and globally and included in the FAS and in the PPS by contrast agent allocated by the randomization and globally.

The tables and the listing that will be displayed are detailed in Sections 6.1.1.3 and 6.2.3.

### 5.2.2. Protocol Deviations

As per International Conference on Harmonization (ICH) E3 guideline [2], a protocol deviation is any change, divergence or departure from the study design or procedures defined in the protocol, with or without impact to the subject safety or the efficacy assessments. Protocol deviations are displayed in the Clinical Study Report (CSR) as a metric of the feasibility and reliability of the study. The list of protocol deviations is presented in the table below and can be updated if necessary before breaking the blind. Protocol deviations will be gathered from monitoring files, clinical database and external vendors of off-site data (imaging, laboratory data, ECG...).

Protocol deviations will be split in major and non major deviations. A major deviation is defined as a deviation having an impact on the primary criteria. A first categorisation is done in this document, then final categorisation will be done before breaking the blind. The decision will be duly described in the meeting minutes.

The deviations are listed in the table below:

Category	Description	Source	Status
Inclusion criteria not met/Non inclusion criteria met	Subject not having reached legal majority age	Clinical data base	Non major
	Subject not presenting, at the time of inclusion, with known or highly suspected focal areas of disrupted Blood Brain Barrier (BBB) (e.g., primary and secondary tumors, focal inflammatory or demyelinating disorders) including at least one expected enhancing lesion of minimum 5 mm (long axis). This lesion must have been detected on a previous imaging procedure (computerized Tomography (CT) or MRI)	Clinical data base	Major
	Subject not scheduled for a routine CNS contrast-enhanced MRI examination for clinical reasons or not agreeing to have a second contrast-enhanced MRI examination for the purpose of the study	Clinical data base	Non major
	Subject not able or not willing to participate to the study	Clinical data base	Non major
	Subject not having provided his/her consent to participate in writing by dating and signing the informed consent prior to any study related procedure being conducted	Clinical data base	Non major

CONFIDENTIAL

## FORM

[REDACTED]

## STATISTICAL ANALYSIS PLAN N° GDX-44-004

VERSION 1.0

DATED: 09JAN2018

Page 20 / 60

	Subject not affiliated to national health insurance according to local regulatory requirements	Clinical data base	Non major
	Subject presenting with acute or chronic Grade III (at least) renal insufficiency, defined as an estimated Glomerular Filtration Rate (eGFR) <60 mL/min/1.73 m  based on two eGFR assessments, one within 7 days before the first study MRI and one the day of the MRI (if any of the eGFR result is < 60 mL/min/1.73m  , the subject is not eligible)	Clinical data base	Non major
	Subject presenting with known class III/IV congestive heart failure according to the New York Heart Association classification (NYHA)	Clinical data base	Non major
	Pregnant or breast-feeding female subject (a female subject of childbearing potential or with amenorrhea for less than 12 months must have a negative urine or serum pregnancy test within 24 hours prior to study MRI and must be using a medically approved contraception method* until the last study visit)	Clinical data base	Non major
	Subject having received any investigational medicinal product within 30 days prior to study entry	Clinical data base	Non major
	Subject previously enrolled in this study	Clinical data base	Non major
	Subject presenting with any contraindication to MRI examinations	Clinical data base	Non major
	Subject with known contra-indication(s) to the use or with known sensitivity to one of the products under investigation or other GBCAs	Clinical data base	Non major
	Subject having received any contrast agent (MRI or CT) within 3 days prior to study products administration, or scheduled to receive any contrast agent during the course of the study or within 24 hours after the second study product administration	Clinical data base	Non major
	Subject having received any treatment or medical procedure within 7 days prior to the first MRI or expected/ scheduled to have a change in any treatment or medical procedure in-between the 2 MRI examinations	Clinical data base	Non major
	Subject with anticipated, current or past condition (medical, psychological, social or geographical) that would compromise the subject's safety or her/his ability to participate in the study	Clinical data base	Non major
	Subject unlikely to comply with the protocol, e.g. uncooperative attitude, inability to return for follow-up visits and/or unlikelihood of completing the study	Clinical data base	Non major
	Subject related to the Investigator or any other study staff or relative directly involved in the study conduct	Clinical data base	Non major

CONFIDENTIAL

FORM

[REDACTED]

## STATISTICAL ANALYSIS PLAN N° GDX-44-004

VERSION 1.0

DATED: 09JAN2018

Page 21 / 60

	Subject presenting with acute relapse of multiple sclerosis	Clinical data base	Non major
	eGFR on local measurements below 60 mL/min/1.73m  at visit 2 or visit 4 and contrast media administration performed	Clinical data base	Non major
	eGFR on central measurements below 60 mL/min/1.73m  at visit 2 or visit 4 and contrast media administration performed	Laboratory data base	Non major
	eGFR on local measurements not performed one day before contrast media administration	Clinical data base	Non major
	eGFR on local measurements at visit 1 not performed within 7 days before first contrast media administration	Clinical data base	Non major
	eGFR method is not accurate	Clinical data base	Non major
	No pregnancy test done 1 day before contrast media administration for female of childbearing potential	Clinical data base	Non major
Study disease diagnosis	Procedure used for documenting at least one enhancing lesion is not provided	Clinical data base	Non major
	Time between procedure used for documenting at least one enhancing lesion and first study procedure is greater than 12 months for Czech Republic (CZ)	Clinical data base	Non major
Imaging	Not matching lesion: among subjects with both MRI examinations done, those without enhancing lesions matching at both examination for all off-site readers	Imaging data base	Major
	Scanner-related deviation from the MRI procedures	Clinical data base	Non major
	Subject-related deviation from the MRI procedures	Clinical data base	Non major
	Anatomy (Brain/Spine) is different between on-site and off-site evaluation	Clinical data base and imaging data base	Non major
	Anatomy is Brain for one period and Spine for the other one in the off-site evaluation for at least one off-site reader	Imaging data base	Non major
	Anatomy is Brain for one period and Spine for the other one in the on-site evaluation	Clinical data base	Non major
	Imaging protocol not respected with major impact on primary criterion	Monitoring	Major
	Imaging protocol not respected with impact on primary criterion	Monitoring	Non major

CONFIDENTIAL	
FORM
 
STATISTICAL ANALYSIS PLAN N° GDX-44-004
 
VERSION 1.0      DATED: 09JAN2018
	[REDACTED]
--------------	---	------------

Subject not withdrawn as per protocol	Stopping rules detected on local measurements and subject not withdrawn: Increase in serum creatinine by more than 25% or 0.5 mg/dL (44 umol/L) compared to the baseline value	Clinical data base	Non major
	Stopping rules detected on central measurements and subject not withdrawn: Increase in serum creatinine by more than 25% or 0.5 mg/dL (44 umol/L) compared to the baseline value	Central laboratory data base	Non major
	Stopping rules detected on central measurements and subject not withdrawn: Increase in cystatin C by more than 25% compared to the baseline value	Central laboratory data base	Non major
	Stopping rules detected on central measurements and subject not withdrawn: triplicate QTc Bazett or QTc Fridericia > 500 ms or in increase of > 60 ms over baseline	Central ECG data base	Non major
	Result of pregnancy test positive and subject not withdrawn	Clinical data base	Non major
Unblinding	Blind not maintained on site	Monitoring	Non major
	Blind not maintained at central reading level	Monitoring	Major
Forbidden concomitant medication	Concomitant medication taken in or medical procedure between the two MRI impacting lesion size based on investigator assessment	Clinical data base	Major
IMP deviation	Subject not allocated in the good stratification factor	Clinical data base and IWRS data base	Non major
	Subject not allocated in the good sequence	Clinical data base and IWRS data base	Major
	Subject having performed MRI examination but not administered with the IMP	Clinical data base	Major
	The IMP volume actually administered is different from the theoretical one from 10 to 20%	Clinical data base and IWRS data base	Non major
	The IMP volume actually administered is different from the theoretical one from more than 20%	Clinical data base and IWRS	Major
	Location of IMP injection site is not adequate	Clinical data base	Non major
	Actual IMP injection rate is not adequate	Clinical data base	Non major
	Temperature excursion for IMP	Monitoring	Non major
	IMP management not appropriate	Monitoring	Non major
	Extravasation	Clinical data base	Major
Missing data	Date of birth is missing	Clinical data base	Non major
	Sex is missing	Clinical data base	Non major
	Height is missing	Clinical data base	Non major
	Race is missing	Clinical data base	Non major
	Physical examination not performed	Clinical data base	Non major
	Blood sample for central laboratory assessment not performed	Clinical data base	Non major

CONFIDENTIAL

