### 6.1 Concomitant Treatments of Special Attention

In order to limit any interference with the safety and efficacy evaluation of Investigational Product, the following precaution and restriction must be considered:

Currently, no treatment has been identified that is capable of preventing an allergic reaction with any gadolinium-based contrast agents. Thus, no pre-treatment of any nature will be recommended before contrast-enhanced MRI. Nevertheless, if the investigator decides to premedicate a subject, the treatment must be documented in the medical file and then in the eCRF.

In general, there are no specific recommendations regarding Gadolinium-Based Contrast Agents, and therefore, no specific hydration procedure is defined in this protocol. Nonetheless, whenever possible, the subject should be encouraged to drink water and other non-alcoholic fluids liberally before and after the injection.

According to current knowledge, there is no other concomitant treatment of special attention in that study. However warnings and precautions for use of the concomitant treatments taken by the subject should be considered.

In addition, no change should occur in any treatment or medical procedure (e.g., chemotherapy, radiotherapy, biopsy or surgery etc...) in-between the two MRIs.

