### 11.2 End of Study Participation for a Subject

Screening failures: Subjects who signed the informed consent form and discontinue before Visit 2 (first contrast agent injection and MRI procedures) will be considered screening failures.

If a subject discontinues before Visit 2, the IWRS must be notified and only the reason for being screening failure will be documented on the source document and in the eCRF (see [section 15.3.2](#))

Criteria for premature discontinuation of subjects:

- Adverse Event (according to the investigator's judgment);
- Withdrawal of subject's consent;
- Subject lost to follow-up (date of last contact will be documented in the medical file and the eCRF). Any effort will be undertaken to know the reason for this loss to follow-up and/or to exclude any adverse reaction as this reason. This will be documented in the medical file;
- Any treatment or medical procedure (e.g. chemotherapy, radiotherapy, biopsy or surgery etc...) between the two MRIs;
- At the discretion of the investigator if, for example, the subject safety or well-being is not compatible with study continuation;

Specific subjects study stopping rules:

If any of the events described below occur, injection of IMPs should not be done and the subject should be discontinued from the study:

- Renal toxicity characterized by an increase in serum creatinine by more than 25% or 0.5 mg/dl (44 µmol/l) and/or an increase in serum cystatin C by more than 25% compared to the baseline value
- QTc Bazett or QTc Fridericia >500 ms or an increase of > 60 ms over baseline
- Any events which investigator or Guerbet considers raising a significant concern

The data to be reported in the eCRF for subjects subsequently discontinuing from the study are detailed in the protocol [section 15.3.2](#).

For subjects withdrawn from the study, all data available at the time of withdrawal will be reported in the medical file and the eCRF (e.g.: inclusion data, safety data, administration data, imaging data, reason for withdrawal...). The investigator must make every effort to collect and record all follow-up safety information (i.e., AEs and injection-site tolerance, as appropriate), unless the subject withdraws consent for further data collection/participation for/in the study.

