## STATISTICAL ANALYSIS PLAN N° GDX-44-004

Page 24 / 60

VERSION 1.0

DATED: 09JAN2018

[REDACTED]

	Prior to MRI blood sample for central laboratory assessment is not drawn before contrast media administration	Clinical data base	Non major
	Prior to MRI urinalysis is not performed before contrast media administration	Clinical data base	Non major
	1 day post MRI blood sample for central laboratory assessment is not drawn the day after contrast media administration	Clinical data base	Non major
	1 day post MRI urinalysis is not performed the day after contrast media administration	Clinical data base	Non major
	Before injection vital sign is not taken before contrast media administration	Clinical data base	Non major
	45-minute after injection vital sign is not taken between 30 and 60 minutes after contrast media administration	Clinical data base	Non major
	Between 2 and 4 hours after injection vital sign is not taken between 2 and 4 hours after contrast media administration	Clinical data base	Non major
	1 day post MRI vital sign is not taken the day after contrast media administration	Clinical data base	Non major
	Before injection ECG is not performed before contrast media administration	Clinical data base	Non major
	45-minute after injection ECG is not performed between 30 and 60 minutes after contrast media administration	Clinical data base	Non major
	Between 2 and 4 hours after injection ECG is not performed between 2 and 4 hours after contrast media administration	Clinical data base	Non major
	1 day post MRI ECG is not performed the day after contrast media administration	Clinical data base	Non major
GCP deviation	ICF deviation	Monitoring	Non major
	Source document management not appropriate	Monitoring	Non major

Subjects presenting at least one protocol deviation with a status major will be excluded from the PPS.

Frequency and percentages of subjects with protocol deviations will be presented breaking down by status (major/non major).

Subjects with major protocol deviations throughout the study causing exclusion from the PPS will be presented by contrast agent and globally on the Extended Set for each subset separately: subjects with at least one major protocol deviation and subjects with each major protocol deviation. Non major protocol deviations will follow the same disposition.

The tables and listings that will be displayed are detailed in Sections 6.1.1.2 and 6.2.2.

CONFIDENTIAL	FORM	
STATISTICAL ANALYSIS PLAN N° GDX-44-004		Page 25 / 60

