### 5.5.1. Primary analysis of the primary criteria

The primary objective of the study is to determine a safe and effective dose of P03277 based on a comparison of CNR between several doses, 0.025, 0.05, 0.1 and 0.2 mmol/kg of P03277 and MultiHance® at 0.1 mmol/kg.

The primary criterion is the CNR calculated from the SI measurement of maximum 3 enhanced lesions by the 3 independent blinded readers. CNR averaged for matching lesions per subject will be used in the primary analysis.

The primary analysis will test differences of means of primary criterion for each dose of P03277 compared to MultiHance® and will be done for each of the 3 independent blinded readers (off-site) using the PPS. Holm's step-down method [1] will be used to address multiplicity testing considering the 4 contrast agents to be tested.

A subject will be analyzed as soon as he has a matching evaluation of the CNR at both MRIs by at least one off-site reader. Therefore the numbers of subjects analyzed by reader may be different.

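### SAP 5.2.2 removes pairs treated between the two scans by judged effect on lesion size, although the endpoint is CNR, so some treated pairs stay in the primary comparison

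*SAP*

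**What the plan says.** The protocol restricts treatment between the two scans in three places, none with a condition on lesion size. Section 6.1 says that "no change should occur in any treatment or medical procedure (e.g., chemotherapy, radiotherapy, biopsy or surgery etc...) in-between the two MRIs". Section 11.2 lists among the criteria for premature discontinuation "Any treatment or medical procedure (e.g. chemotherapy, radiotherapy, biopsy or surgery etc...) between the two MRIs". Non-inclusion criterion 9 bars recent treatment and any expected or scheduled change between the scans.

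SAP 5.2.2 turns this into deviation rows. Under the category for forbidden concomitant medication, the single row is "Concomitant medication taken in or medical procedure between the two MRI impacting lesion size based on investigator assessment", graded Major. Breach of criterion 9 ("Subject having received any treatment or medical procedure within 7 days prior to the first MRI or expected/ scheduled to have a change") is graded Non major. The general rule in the same section is that "A major deviation is defined as a deviation having an impact on the primary criteria".

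The grading has a direct consequence: "Subjects presenting at least one protocol deviation with a status major will be excluded from the PPS". The primary analysis (SAP 5.5.1) "will be done for each of the 3 independent blinded readers (off-site) using the PPS", and "CNR averaged for matching lesions per subject will be used in the primary analysis".

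**The concern.** The exclusion row tests a different variable from the one analysed. CNR is lesion signal minus healthy-tissue signal, divided by the standard deviation of background noise (SAP 2.2.1). Lesion size does not enter it. A treatment judged not to have changed size could still have changed signal, and the row does not ask about that.

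The crossover compares two agents in the same lesion and relies on the lesion being the same on both occasions. Where treatment has altered enhancement between visits, the paired difference mixes that change with the difference between agents. The mixture enters the test that decides superiority for each dose and reader.

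**Working it through.** **1. Trigger against definition.** The SAP's general definition of Major is impact on the primary criterion. The treatment row requires impact on lesion size, judged by the investigator. Protocol 6.1 and 11.2 have neither condition. In the same table, the Major row for departures from the imaging protocol is worded in terms of the primary criterion, so suitable wording was already in use.

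**2. A subject treated between scans, followed through the rules.**

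- Withdrawn under 11.2 before scan 2: the row for an MRI not performed is Major, so the subject leaves the PPS.
- Scanned twice, size effect judged present: Major, leaves the PPS.
- Scanned twice, no matching enhancing lesion for any off-site reader: Major, leaves the PPS.
- Scanned twice, lesions matched, no judged size effect, change expected or scheduled at inclusion: Non major under criterion 9. Recorded, but stays in the PPS.
- The same, but treatment unplanned: no row applies. The block for subjects not withdrawn as per protocol covers creatinine, cystatin C, QTc and pregnancy, and omits the 11.2 treatment criterion. The subject stays in the PPS.

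The last two cases are the gap.

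**3. Other analyses.** The model has terms for agent, period and pre-contrast CNR (SAP 5.5.1.2 and 5.5.1.3), and none for treatment between scans. The FAS repeat (5.5.2.1) keeps these pairs. The sensitivity analysis in 5.5.2.4 selects on ROI placement. No planned analysis removes them.

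**4. Possible size.** The plan's 50 per group (SAP 3.3) cannot be reproduced, because the control mean CNR is not given. For illustration it can be solved for. Inputs from SAP 3.3: SD 3.01, n = 50, power 90%, a 30% increase, one-sided 0.025. Assumptions: 3.01 is the SD of paired differences, and the test is at the first Holm step, 0.025/4 = 0.00625. Then

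difference = (3.01/√50) × (2.498 + 1.282) = 1.609, and control mean = 1.609/0.3 = 5.36.

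With μ0 = 5.36, μi = 1.3 × 5.36 = 6.968 and the true difference is 1.608. Paired-t power is 0.877 (the 90% came from the normal approximation).

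Let a share f of pairs have second-scan CNR lowered by a fraction r. Both values are assumed, and the SD is held at 3.01. The expected differences are:

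- order balanced among affected pairs: (μi − μ0)(1 − f·r/2)
- all affected pairs with P03277 second: (μi − μ0) − f·r·μi
- all affected pairs with MultiHance second: (μi − μ0) + f·r·μ0

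| f, r | Balanced (power) | All P03277 second (power) | All MultiHance second |
|---|---|---|---|
| 5%, 20% | 1.600 (0.873) | 1.538 (0.841) | 1.662 |
| 10%, 40% | 1.576 (0.861) | 1.329 (0.700) | 1.822 |
| 20%, 40% | 1.544 (0.844) | 1.051 (0.457) | 2.037 |

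Balanced attenuation is f·r/2: 0.05 × 0.20/2 = 0.5% up to 0.20 × 0.40/2 = 4%. It does not depend on the control mean. The two right-hand columns are limits in which every affected pair falls in one sequence.

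**The case against.** A reader might infer that the size row is the only way a treated subject leaves the PPS. The documents do not support that. Protocol 11.2 already makes such treatment a criterion for discontinuation, and a subject withdrawn before scan 2 is removed by the row for an MRI not performed. The gap concerns only treated subjects who were not withdrawn.

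A reader might also infer that all these pairs go unrecorded. An expected or scheduled change is a listed deviation, and Non major deviations are tabulated. Concomitant medications are summarised and listed (SAP 5.6.6), although the categories there are set by when a medication ended, so a drug started between scans and still ongoing is grouped with long-standing ones. Only unplanned treatment has no deviation row.

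SAP 5.2.2 calls its grading a first categorisation, allows the list to be updated, and requires a minuted final categorisation before the blind is broken. This is a fair point: the process for a correction exists, and under the general definition the sponsor could reach the right result. It does not make the written row correct, and a review that follows the row as worded would ask about size.

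On impact, order is randomised (protocol 5.3.1) and period is in the model. If exactly five pairs were affected and 1:1 order were unrelated to being affected, all five would share an order with probability 2 × (1/2)^5 = 1/16. The one-sequence columns above are therefore limits, not expectations.

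Two further arguments are tempting and should be left out. One is that particular drugs change enhancement within days while size stays constant. The other is that investigators' size judgements are unreliable across agents and doses. The documents give no evidence for the first and do not describe how size is to be judged. The mismatch between row and definition stands without either.

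**Conclusion.** The inconsistency is real and worth correcting before unblinding. For treatment between scans, the stated rule uses lesion size where the SAP's own definition calls for the primary criterion. Treated subjects with two scans and no judged size effect stay in the primary comparison, and no planned analysis shows the result without them.

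The likely consequence is modest: added noise, and attenuation of about 0.5% to 4% under the assumed 5% to 20% of pairs and a 20% to 40% fall in second-scan CNR. Material bias, in either direction, requires affected pairs to be unbalanced across sequences. The balanced figure assumes that treatment between scans is unrelated to which agent came first; the documents give no information on that or on the number of subjects. They do not support a claim that the superiority result is biased.

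**What to change.** In SAP 5.2.2:

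- In the treatment row, replace the condition on lesion size and investigator assessment with: *with potential impact on the primary criterion (CNR), judged at the blinded data review before unblinding*. Keep it Major.
- Add a deviation row for any treatment or procedure between the MRIs where the subject was not discontinued.
- Judge breaches of non-inclusion criterion 9 on the same basis, instead of grading them all Non major.
- Add a sensitivity analysis that repeats the primary model without all pairs treated between scans.

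Protocol 6.1, protocol 11.2 and the SAP row must be reconciled on how these subjects are classified. Section 6.1 speaks of a change in treatment, 11.2 of any treatment, and the SAP of treatment affecting size. Without one definition, the set dropped in the sensitivity analysis is undefined. This is a matter of classification for analysis; no clinical rule needs to change.

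The cost is SAP wording, one item at the blinded review and one further run of an existing model. The downside is a somewhat wider, judgement-based exclusion after randomisation: a few subjects may leave the PPS. They remain in the FAS analysis, and the judgement is made blind.
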